## AMENDMENT HISTORY

Updated to reflect the most recent protocol version, EDMS-ERI-148527695, 15.0

**SAP version 2.0** was created to reflect some minor corrections from the submission team.

**SAP version 3.0** was created to reflect the changes in study design, described in protocol amendments 1 to 2.

**SAP version 4.0** was created to add analysis period of the study. The treatment phase includes an initial 24 week treatment period and a treatment extension period of 24 weeks, described in protocol amendments 3 to 4.

**SAP version 5.0** was created to finalize as no further comments received.

Protocol Version	Issue Date
Original Protocol	20 October 2017
Amendment 1	18 December 2017
Amendment 2	06 Mars 2018
Amendment 3	18 June 2018
Amendment 4	21 February 2019
Amendment 5	2 August 2019

### Amendment 1 (18 December 2017)

**The overall reason for the amendment:** Health Authority feedback regarding follow-up treatment and safety monitoring after the 24-week treatment period, and hormonal contraceptive treatment have been incorporated (detailed below).

- Clarification that, after the 24-week JNJ-56136379 treatment period, NA treatment (ETV [entecavir] or TDF [tenofovir disoproxil fumarate]) will be continued or started based on local treatment guidelines, ensuring subjects qualifying for Hepatitis B Virus (HBV) treatment are treated adequately.
- Recommendation that subjects not continuing or starting NA treatment should be followed up by their primary care physician, outside of the study, for an additional 24 weeks after the 24-week follow-up phase in the study (as per local treatment guidelines). This should ensure adequate safety monitoring for subjects not on HBV treatment.
- As oral contraceptive (OC) treatment is associated with potential risks, such as venous thrombosis, and these risks have been reported to be highest during the first 3 months of treatment, female subjects on OC treatment, can only be included in the study if at time of screening they have been on a stable OC treatment regimen for at least 3 months, without any safety concerns. Furthermore, given the observed

---

increase in EE exposure in combination with JNJ-56136379, stable OC treatment regimens including EE are only allowed at the lowest commercially available EE dose, i.e. 20 µg, to minimize any potential safety risks. If female subjects start OC treatment during the study, OC treatment regimens should not include EE, to minimize any potential safety risks due to the observed increase in EE exposure in combination with JNJ-56136379.

- Severity of AEs will be assessed based on the standardized DAIDS Toxicity Grading Scale, in line with laboratory abnormalities assessment.
- The response criterion for continuation in the treatment extension study has been reworded; subjects who have completed 24 weeks of treatment and who have HBV DNA levels <LLOQ at Week 20, with or without evidence of HBsAg decline will participate in the treatment extension study.
- Addition that choice of ETV or TDF by investigator is per local practice, ensuring consistency throughout the protocol.
- As the age of legal consent in certain countries is > 18 years, the inclusion criterion regarding minimum age in the study is updated to clarify this.
- Clarification on instructions in case of missed dose
- Removal of verapamil and felodipine from list of concomitant therapy to be used with caution as these are on the list of disallowed concomitant medication.
- Corrections to assessments during the follow-up phase ensuring consistency with treatment phase:
- Fibroscan assessment as part of efficacy evaluations to be performed only in subjects in the PK substudy.
- Triplicate ECGs to be performed.
- Clarification that ECGs will be read centrally. However, on Day 1, pre-dose ECG assessment will also be done locally on-site to determine eligibility.
- Correction of recommendations in case of specific toxicities, ensuring consistency with the treatment discontinuation and study withdrawal criteria.
- Clarification added that returned NA treatment can be re-dispensed to the same subject.
- Replacement of incorrect version of EQ-5D-5L (tablet version rather than paper version)

---

- Replacement of incorrect version of SF-36v2 (2010 version rather than 2000 version)
- Minor updates of abbreviation for entecavir corrected (ETV rather than ETF)
- Minor updates of IB addendum reference updated with final date

#### **Amendment 2 (06 March 2018)**

**The overall reason for the amendment:** Considering Health Authority recommendation to evaluate the effect of extended treatment on hepatitis B surface antigen (HBsAg) decline, the treatment duration will be extended to 48 weeks in subjects with virologic response who did not experience any safety concerns during the first 24 weeks of treatment that preclude continued study drug treatment as determined by the investigator.

#### **Amendment 3 (18 June 2018)**

The overall reasons for the current amendment are the selection of the high dose to be administered in Part B of the study, and an update of the available clinical data on JNJ-56136379.

#### **Amendment 3 /JPN-1 (28 June 2018)**

The overall reason for the current amendment was that HBcrAg is an important marker used for patient management in Japan and thus, as recommended by Japanese treatment guidelines for chronic hepatitis B, HBcrAg results at Week 40 may also be used to support the decision to stop all treatment after completion of 48 weeks of treatment.

#### **Amendment 4 (18 June 2018)**

The Sponsor has decided to stop further dosing of subjects with JNJ-56136379 in the open-label 75 mg monotherapy arm, upon recommendation from the Data Review Committee (DRC).

In addition, the Sponsor has limited the duration of JNJ-56136379 250 mg monotherapy to 24 weeks. Subjects in the 250 mg monotherapy arm eligible for treatment extension, will receive JNJ-56136379 in combination with nucleos(t)ide analog (NA) treatment from Week 24 to Week 48, limiting the duration of JNJ-56136379 monotherapy.

---

## ABBREVIATIONS

ADaM	Analysis Data Model
AE	Adverse Event
ALT	Alanine Aminotransferase
ANCOVA	Analysis of Covariance
Anti-HBe	Hepatitis B e Antibody
Anti-HBs	Hepatitis B surface Antibody
ATC	Anatomical Therapeutic Chemical
BCP	Basal Core Promoter
BMI	Body Mass Index
CHB	Chronic Hepatitis B
CI	Confidence Interval
CRF	Case Report Form
CSR	Clinical Study Report
CTP	Clinical Trial Protocol
DAIDS	Division of AIDS
DBP	Diastolic Blood Pressure
DPS	Data Presentation Specifications
DRC	Data Review Committee
ECG	Electrocardiogram
eCRF	Electronic Case Report Form
EOS	End of study
EOT	End of treatment
ESI	Event of special interest
ETV	Entecavir
HBcrAg	Hepatitis B core related Antigen
HBeAg	Hepatitis B e Antigen
HBsAg	Hepatitis B surface Antigen
HBV	Hepatitis B Virus
HIV	Human Immunodeficiency Virus
HR	Heart Rate
ICH	International Conference on Harmonization
ITT	Intent-to-Treat
IU	International Unit
LLOQ	Lower Limit of Quantification
LS	Least Squares
MedDRA	Medical Dictionary for Regulatory Activities
MMRM	Mixed effects Model for Repeated Measures
NA	Nucleos(t)ide Analogue
NAP	Not applicable
NAV	Not available
NUC	Nucleos(t)ide
PC	Precore

---

PD	Pharmacodynamic
PK	Pharmacokinetic(s)
PR/PQ	Interval between onset of P wave and onset of QRS complex
QRS	Begins at the onset of Q wave and ends at endpoint of S wave
QT	Begins at the onset of QRS complex and ends at endpoint of T wave
QTc	Corrected QT interval
QTcB	QT corrected by Bazett's formula
QTcF	QT corrected by Fridericia's formula
RR	Interval between R wave of one heartbeat and R wave of preceding heartbeat
SAE	Serious Adverse Event
SAP	Statistical Analysis Plan
SBP	Systolic Blood Pressure
SD	Standard Deviation
SDTM	Study Data Tabulation Model
SE	Standard Error
TDF	Tenofovir Disoproxil Fumarate
TEAE	Treatment emergent-adverse events
DPS	Data Presentation Specification
WHO	World Health Organization

## 1. INTRODUCTION

This statistical analysis plan (SAP) for the 56136379HPB2001 phase 2 trial (both part A and B) describes the statistical analysis to assess the efficacy and safety of JNJ-56136379 as Monotherapy and in Combination with a Nucleos(t)ide Analog (NA) in subjects with Chronic Hepatitis B Virus Infection. This SAP will also be used for the interim analyses that may be performed in this study when at least 80% of subjects have completed visits at Week 12, Week 24, Week 48 and when all subjects have completed the Follow-up Week 12. The interim analyses will present a subset of the output meant for the final analysis. The SAP specifies the analysis displays to be presented and describes the methods and procedures in a more elaborated way than in the statistical methods section of the protocol.

The pharmacokinetics analysis of this study will be described and reported in the PK/PD report.

The statistical analysis will be performed using SAS® (version 9.2 or higher) and for dose response modeling also the Proc MCPMod from Citel for SAS will be used for which the versions will be clearly described.

---

The statistical principles applied in the design and planned analyses of this study are consistent with International Conference on Harmonization (ICH) E9 guidelines.

No adjustments for multiplicity will be performed.

Minor modifications may be necessary to the planned design of tables, figures, and listings to accommodate data collected during the actual study conduct. Any major deviations from the final approved SAP or additional unplanned analyses will be documented (with justification) in a revised version of the plan approved prior to the primary analysis or will be documented in the Clinical Study Report (CSR).

[figure not shown]
### **1.1. Trial Objectives and Endpoints**

See Clinical Trial Protocol (CTP), Section 2.1.

### **1.2. Trial Design**

[figure not shown]
See CTP, Section 3.1. The schematic overview of the study design provided in the protocol is reproduced below.

**Figure 1: High-level Overview of the Study Design**

a Per Protocol Amendment 4, subjects in the JNJ-56136379 250 mg monotherapy arm (Treatment Arm 6) who are eligible for treatment extension, based on the treatment extension criteria assessed at Week 20, will receive JNJ-56136379 in combination with NA treatment from Week 24 to Week 48.

**Figure 2: Schematic Overview of the Study**

---

Abbreviations: FA: final analysis; IA: interim analysis; JNJ-379: JNJ-56136379; NA: nucleos(t)ide analog.

a , Subjects who have successfully completed 24 weeks of treatment, have HBV DNA levels <LLOQ by Week 20 and who did not experience any safety concern that would preclude continued study drug treatment will receive another 24 weeks of study treatment in the extension phase. For all other subjects, NA treatment (either ETV or TDF as per local practice) should be continued or, in case of JNJ-56136379 monotherapy during the 24-week treatment phase, started at Week 24 as per local treatment guidelines. An additional 24-week follow-up (as per local treatment guidelines), by their primary care physician outside of the study, is recommended after the 24-week follow-up phase in the study (FU Schedule 1), for subjects who do not continue or start NA treatment at Week 24.

b After completion of 48 weeks of study treatment, a subject will complete all treatment if all of the Individual Subject Treatment Completion Criteria (see Section 6.2) are met. For these subjects, follow-up assessments will be obtained until 48 weeks after EOT (FU Schedule 2). A Subject should re-start NA treatment (ETV or TDF) during the 48 weeks of post-treatment follow-up (FU Schedule 2) if he/she meets one of the criteria described in Section 6.3. Subjects who do not meet the Individual Subject Treatment Completion Criteria after 48 weeks of study treatment, should continue or, in case of JNJ-56136379 monotherapy, start NA treatment as per local treatment guidelines. For these subjects, follow-up assessments will be obtained until 24 weeks after EOT (FU Schedule 1). For subjects who do not continue or start NA treatment at Week 48, an additional 24-week follow-up (as per local treatment guidelines), by their primary care physician outside of the study, is recommended after the 24-week follow-up phase in the study.

c The sponsor, in agreement with the DRC, will select the dose for Part B which will be based on all available clinical safety data of JNJ-56136379 following the completion of the dose evaluation in the Phase 1b study 56136379HPB1001. This dose will not exceed the highest dose evaluated in study 56136379HPB1001, i.e., 250 mg once daily.

### **1.3. Protocol Amendments**

This SAP was prepared based on the trial protocol number EDMS-ERI-148527695, 13.0

### **1.4. Statistical Hypotheses for Trial Objectives**

As this is an exploratory, hypothesis-generating study, no formal statistical hypothesis testing will be performed.

### **1.5. Sample Size Justification**

See CTP, Section 11.2.

### **1.6. Randomization and Blinding**

See CTP, Section 5.

## **2. GENERAL ANALYSIS DEFINITIONS**

The SAP will use throughout the document the following definitions:

- *Treatment* includes JNJ-56136379, placebo and NA (ETV or TDF)
- *Study agent* includes JNJ-56136379 and placebo
- *NA* includes NA (ETV or TDF)

### **2.1. Analysis Sets**

*Screened Population or all subjects* consists of all subjects, i.e. screening failures and (not) randomized subjects.

---

*Safety population* consists of all subjects who received at least one dose of the study agent and all safety endpoints will be analyzed by the treatment arm as treated.

*Intent-to-Treat Population (ITT)*: all subjects who are randomized and received at least one dose of any study agent. If a subject receives a study agent other than their randomly assigned study agent, subjects will be shown in the treatment arm as randomized.

The analysis population will be indicated in the title of each table and listing.

## **2.2. Definition of Baseline**

The last observed measurement before the date and time of the first administration of the study agent will be considered the baseline measurement.

In case the first administration time and/or the measurement time is missing, the day 1 measurement will be considered as baseline measurement. The underlying assumption is that the protocol is followed which states that day 1 samples are to be collected before the first dose of study drugs.

## **2.3. Definition of Analysis Phases, Periods, Types of Follow-up, Time Points and Visit Windows**

Analysis phase allocation will be included for all part of the analysis if applicable. The analysis periods and follow-up types will be presented in the efficacy part and the safety part (except for adverse events) of the analysis and in the general output if mentioned.

The analysis phase and periods and analysis time points are presented in the table 1 and table 2 below.

The procedures to be performed throughout the study at each time point are outlined in the time and events schedule in appendix 4, appendix 5 and appendix 6 of this document.

**Table 1: Construction of phases**

Analysis phase	Analysis Period	Start date	End date
Screening (phase 1)		The date of signing the informed consent	1 day before the first study agent intake
Treatment (phase 2)	Initial Treatment	Date of first study agent intake	- If not included in the treatment extension°: Date of last study agent intake + 5 days*

Analysis phase	Analysis Period	Start date	End date
	(period 1)		- If included in the treatment extension o : Date of Week 24 study agent intake+5 days #
	Treatment Extension (period 2)	End of the initial treatment period + 1 day	Date of last study agent intake + 5 days*
Follow-up (phase 3)		End of the treatment phase +1 day	Trial termination date (date of last contact) or cut-off date for an interim analysis, whichever comes first

o depending on the answer in the FA dataset: FAOBJ = " WILL THE SUBJECT CONTINUE TREATMENT IN TREATMENT EXTENSION PHASE?" and whether actually treatment was extended in the EX dataset.

\* or study termination date (date of last contact) or cut-off date for an interim analysis, whichever comes first.

# Date of the Week 24 visit included the EX dataset.

Note: The last phase, whichever it is for a subject, always ends on the day of trial termination (last contact) or the cut-off date in case the data are analysed for an interim or DRC analysis (whichever comes first).

There are two types of follow-up in this study defined (FAOBJ = 'DID THE SUBJECT MEET ALL THE TREATMENT COMPLETION CRITERIA AS PER PROTOCOL?'):

- Treatment free: subjects meeting the criteria mentioned in CTP section 6.3 and therefore subject will start follow-up phase without NA treatment.
- NA follow-up: subjects not meeting the criteria mentioned in CTP section 6.3 and therefore subject will start/continue follow-up phase with NA treatment.

For analyses that require a particular visit, the Time Point Window and Visit Window are defined in the table 2 as below.

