
 
• To evaluate the frequency of sustained off-treatment response.
 
	
 
• Proportion of subjects with sustained reduction/suppression and/or sero-clearance considering single and multiple markers such as HBsAg, HBeAg, HBV DNA and ALT levels at FU Week 12, 24 and 48.
 

 
• To evaluate the frequency of virologic and clinical relapse after EOT.
 
	
 
• Proportion of subjects with virologic relapse defined as confirmed post-treatment increases in HBV DNA <math>>2,000</math> IU/mL after having met the treatment completion criteria.
 
• Proportion of subjects with clinical relapse defined as confirmed post-treatment increases in HBV DNA <math>>2,000</math> IU/mL after having met the treatment completion criteria, in association with confirmed ALT value <math>>2 \times</math> ULN.
 

 
• To evaluate the proportion of subjects requiring NA re-treatment during follow-up.
 
	
 
• Proportion of subjects who meet the re-treatment criteria as outlined in Section 6.4.
 

 
• To evaluate the efficacy of NA re-treatment during follow-up.
 
	
 
• Proportion of subjects with decline in HBV DNA, ALT and/or HBsAg levels after re-start of NA treatment during follow-up.
 

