#### **6.4. Re-treatment Criteria During Follow-up**

Subjects who met the Subject Treatment Completion Criteria in Section 6.3 should start either ETV or TDF treatment during the post-treatment follow-up, according to local standard of care, in the following cases:

- Confirmed post-treatment increases in HBV DNA  $>2,000$  IU/mL and ALT  $>2 \times$  ULN, OR
- Confirmed post-treatment increases in HBV DNA  $>20,000$  IU/mL, OR
- In the event of worsening signs of liver function during follow-up assessments.

**Note:** It is recommended that the original HBV DNA and/or ALT test and the corresponding confirmation test used to decide on re-treatment are at least 4 weeks apart. Confirmation tests and initiation of re-treatment within 4 weeks are at the discretion of the investigator.

**Note:** The investigator should contact the sponsor in case re-treatment will be initiated.

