### 5.2.1 Parameter Definitions

The following parameters will be derived as follows:

*Viral breakthrough during 24 weeks of treatment (all subjects), during 48 weeks of treatment (subject with treatment extension) and during NA follow up for all subject who switch to NA-treatment during follow-up:*

HBV virological breakthrough is defined as having a confirmed on-treatment HBV DNA increase by  $>1$  log10 from nadir level (lowest level reached during 24/48 weeks treatment) or a confirmed on-treatment HBV DNA level  $>200$  IU/mL in subjects who had HBV DNA level below the lower limit of quantification (LLOQ) of the HBV DNA assay.

The proportion of subjects with a viral breakthrough is defined as follows:

---

- 0 (No) = subject has not had a viral breakthrough (see definition above) up to the considered time point
- 1 (Yes) = subject has a viral breakthrough at the considered time point or has had a viral breakthrough before (regardless of the HBV DNA result at the considered time point)
- 2 (No: ongoing): subject has not had a viral breakthrough (see definition above) up to the last time point but is still ongoing (only for interim analysis)

Confirmed means that the criterion should be fulfilled at 2 or more consecutive time points or at the last observed time point on-treatment. On-treatment means in the treatment phase, except for the baseline record.

The proportion of subjects with a viral breakthrough during initial 24- or 48-weeks treatment but still on NA Treatment (Yes / No)

Note: For Viral breakthrough during NA follow up, only subject on NA treatment will be include in the denominator.

*Viral relapse* is defined in the follow-up phase as follows:

- 1 (Yes) = viral relapse: confirmed  $\geq 2000$  IU/mL quantifiable.
- 0 (No) = no viral relapse: at least one post-treatment measurement available and not a viral relapse
- 2 (Not applicable) = no post-treatment HBV DNA measurements available
- 3 (No: ongoing) = no viral relapse: at least one post-treatment measurement available and not a viral relapse but still ongoing (only for interim analysis)

Confirmed means that the criterion should be fulfilled at 2 or more consecutive time points or at the last observed time point.

Note: viral relapse will only be assessed for those subjects who at the actual end of treatment have HBV DNA  $< 20$  IU/ml detectable/ undetectable.

*Biochemical relapse* is defined in the follow-up phase as follows:

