**Table 4: response categories for viral activity parameters**

	Category criteria	Additional info
HBsAg Response	Subject who has achieved a HbsAg level <1000 IU/mL per time point	These proportions will also be included per analysis phase and analysis period. A subject will be included in the numerator if the response category is at least once met within the analysis phase/period.
	Subject who has achieved a HbsAg level <100 IU/mL per time point	
	Subject who has achieved a HbsAg level <10 IU/mL per time point	
	Subject who has achieved a HbsAg level <0.05 IU/mL per time point	
HBV DNA Response	Subject who has achieved a HBV DNA level <1 log10 IU/mL per time point	These proportions will also be included per analysis phase and analysis period. A subject will be included in the numerator if the response category is at least once met within the analysis phase/period.
	Subject who has achieved a HBV DNA level <2 log10 IU/mL per time point	
	Subject who has achieved a HBV DNA level <3 log10 IU/mL per time point	
	Subject who has achieved a HBV DNA level <20 IU/mL per time point	
	Subject who has achieved a HBV DNA level <60 IU/mL per time point	
	Subject who has achieved a HBV DNA level <100 IU/mL per time point	
	Subject who has achieved a HBV DNA level <1000 IU/mL per time point	
	Subject who has achieved a HBV DNA level <2000 IU/mL per time point	
	Subject who has achieved a HBV DNA level <20000 IU/mL per time point	
	Subject who has achieved a HBV DNA level < LLQ for target detected and not detected per time point	
	Subject who has achieved a HBV DNA level < LLQ for target not detected per time point	
	Subject who has achieved a HBV DNA level < LLQ for target detected per time point	
HBV RNA Response	Subject who has achieved a HBV RNA level <100 cp/mL per time point	These proportions will also be included per analysis phase and analysis period. A subject will be included in the numerator if the response category is at least once met within the analysis phase/period.
	Subject who has achieved a HBV RNA level <1000 cp/mL per time point	
	Subject who has achieved a HBV RNA level <2000 cp/mL per time point	
	Subject who has achieved a HBV RNA level <20000 cp/mL per time point	
	Subject who has achieved HBV RNA target not detected per time point	
	Subject who has achieved HBV RNA < LLOQ per time point	
	Subject who has achieved a HBV RNA level <250 cp/mL at week 24	

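### The SAP has no rule for data after NA re-start in treatment-free follow-up and no derivation of sustained off-treatment response

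*SAP*

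**What the plan says.** SAP 2.3 defines two follow-up types. The first is "Treatment free: subjects meeting the criteria mentioned in CTP section 6.3 and therefore subject will start follow-up phase without NA treatment". The second, NA follow-up, is for subjects who did not meet those criteria. Both describe how follow-up begins. Under SAP Table 1 the follow-up phase ends at "Trial termination date (date of last contact) or cut-off date for an interim analysis, whichever comes first", so an NA re-start neither closes it nor changes the type.

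Protocol 6.4 plans re-starts in exactly the treatment-free group. Subjects who met the completion criteria and later meet a re-treatment criterion "should start either ETV or TDF treatment during the post-treatment follow-up, according to local standard of care".

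SAP section 5 presents virology and serology by phase, period, follow-up type and time point. SAP 5.3 tabulates the response categories by time point and also by phase or period. For the second display, Table 4 says: "A subject will be included in the numerator if the response category is at least once met within the analysis phase/period". Table 5 censors subjects without an event at their last assessment of the marker, with no mention of NA re-start.

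For the extension phase, protocol 2.1 lists "Proportion of subjects with sustained reduction/suppression and/or sero-clearance considering single and multiple markers" at FU Weeks 12, 24 and 48. It lists the need for re-treatment, and the response after re-treatment, as two further endpoints. SAP 1.1 refers back to the protocol for endpoints, and SAP 5.3 derives none of the three.

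**The concern.** The extension phase asks whether treatment can be finite (protocol 1.4 and the study design rationale in 3.1). That question needs the share of completers who hold their response without NA. A table headed treatment-free that includes viral loads measured after NA was resumed does not give that share. The error runs one way: re-suppression can only raise the response rate.

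The per-phase display has a different weakness. Completers enter follow-up with HBV DNA below LLOQ at Week 40, confirmed at Week 44 (protocol 6.3). One early follow-up visit is then likely to satisfy the rule, whatever happens afterwards. Completers may also be few, in which case each such subject moves the rate noticeably.

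**Working it through.** No sample size, power or alpha in the plan depends on this point, so there is no stated figure to reproduce. The check is a reading of the rules on one subject, followed by an illustration.

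**One subject followed through the rules (hypothetical values).** A completer has HBV DNA <20 IU/mL at FU Week 4, reaches 50,000 IU/mL confirmed by FU Week 16, re-starts NA under protocol 6.4, and is <20 IU/mL at FU Week 48.
- Follow-up type (SAP 2.3): treatment-free throughout.
- Response at FU Week 48 (Table 4, by time point): counted, although on NA.
- Response over the phase (Table 4, at least one visit): counted, already because of FU Week 4.
- Viral relapse and post-treatment failure (SAP 5.3): both yes, given HBV DNA <20 IU/mL at end of treatment and at Weeks 40 and 44.

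The subject is thus a relapser in one table and a treatment-free responder in another.

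**Effect on response at a visit.** Let r be the share of treatment-free subjects who relapse and q the share of relapsers re-started on NA and re-suppressed by the visit. Both are assumptions. Non-relapsers are taken as responders, and other relapsers as non-responders.
- Response without NA = 1 − r
- Response reported under the SAP as written = (1 − r) + r × q

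| r | without NA | reported, q = 50% | q = 80% | q = 100% |
|---|---|---|---|---|
| 30% | 70% | 85% | 94% | 100% |
| 50% | 50% | 75% | 90% | 100% |
| 70% | 30% | 65% | 86% | 100% |

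For example, r = 50% and q = 50% gives 0.50 + 0.50 × 0.50 = 0.75.

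**Effect on the per-phase display.** Let f be the share of relapsers never <20 IU/mL in follow-up before re-start.
- Met at least once, counting only values off NA = (1 − r) + r(1 − f)
- Met at least once over the whole phase = (1 − r) + r(1 − f) + r × f × q

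With f = 0 both are 100% for any r, so rescue adds nothing and the figure says nothing about durability. With r = 50% and f = 50%, the off-NA figure is 0.50 + 0.25 = 75%. The whole-phase figure is 0.75 + 0.25 × q, which is 95% at q = 80% and 100% at q = 100%. The per-phase rule therefore mostly credits suppression before relapse. The missing NA rule acts mainly on results by visit.

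**Time to event.** Table 5 does not censor at re-start, so values on NA can supply events. It also gives no time origin. If time runs from first dose, most HBV DNA events in completers will have occurred on treatment, and the effect here is small.

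**The case against.** The SAP does not lose sight of relapse. It defines viral, biochemical and clinical relapse, has a specific post-treatment failure outcome for treatment-free follow-up, and lists subjects with viral relapse. NA rescue medication is tabulated and listed (SAP 4.4). For viral breakthrough, SAP 5.3 recognises subjects who switch to NA during follow-up and restricts that denominator to subjects on NA. Table 4 is a generic display, and the study is exploratory with no formal hypothesis testing.

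All of this is correct, but none of it changes a response numerator. The breakthrough rule also sits awkwardly with SAP 2.3: the same subject is in NA follow-up for breakthrough and treatment-free for response.

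A reader might go further in four ways that the documents do not support.
- *Rescued relapsers are reported as off-treatment responders.* No output carries that name, and a confirmed relapser also appears under relapse and failure. The gap is the missing derivation.
- *Rescue drives the at-least-once figure.* As shown in the working, suppression before relapse mostly does.
- *NA rescue hides relapse.* SAP 5.3 says: "Confirmed means that the criterion should be fulfilled at 2 or more consecutive time points or at the last observed time point". A retest 28 days after an on-target FU Week 32 visit (day 219) falls on day 247, the last day of the 192 to 247 window, and would lose to the day-219 value if one value per window were used. But SAP 2.3 limits that selection to descriptive statistics, tabulations per time point and graphics, and does not say that it governs confirmation. This is an ambiguity that one sentence removes.
- *HBsAg response is equally affected.* The SAP's own prior means for 24-week HBsAg change on NA are about −0.01 log10 IU/mL (untreated HBeAg-negative) and −0.06 (suppressed) in Table 3. The point is essentially about HBV DNA.

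**Conclusion.** The point holds in a limited form. Followed exactly, the SAP gives HBV DNA response rates for treatment-free follow-up that mix data on and off NA, and it does not derive the protocol's sustained off-treatment response. In the illustration, FU Week 48 response is overstated by r × q: 15 to 30 percentage points at 30% relapse, 25 to 50 at 50%, and 35 to 70 at 70%, for q from 50 to 100%. These sizes rest wholly on assumed rates; the true effect could be small if few completers relapse or re-start. The fixed follow-up group in SAP 2.3 is not itself the fault, because it supplies the right denominator. Relapse reporting and the Week 24 primary endpoint are unaffected. This is a cheap improvement to a descriptive extension-phase analysis, and it does not question the clinical re-treatment criteria.

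**What to change.** In SAP 2.3 and 5.3:
- Keep every subject who met the completion criteria as the fixed denominator of the treatment-free group. Do not move records after re-start into NA follow-up: that would drop relapsers from the denominator, and if all relapsers re-start, the rate becomes (1 − r)/(1 − r) = 100%.
- Derive sustained off-treatment response at FU Weeks 12, 24 and 48 as: criterion met at that visit, no earlier confirmed relapse, and no NA re-start. Count NA re-start as non-response at all later visits.
- Do not use the at-least-once rule for off-treatment response.
- Flag records after NA re-start, and report the need for re-treatment and the response after it separately, as protocol 2.1 lists them.
- State that relapse confirmation uses all measurements, including unscheduled retests.

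The cost is SAP wording and a little programming. NA dispensing in follow-up (protocol Schedule 2) and NA administration and rescue medication (SAP 4.6 and 4.4) are already captured. The reported off-treatment response rate may be lower.
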